**Brief Intervention for Justice-Involved Substance Users:
Harnessing Mechanisms of Change**

NCT03308877

04/01/2017

Study Design

D.3. Overview. We propose a rigorous RCT using a matched-pairs design to test *a priori* hypotheses based on the findings of Preliminary Study 2, while investigating the mechanisms by which people change. In line with renewed national efforts to promote reproducible science, this study is, among other things, an attempt to replicate the primary findings of our published work in a larger sample. We incorporate appropriate blinding, and validated, multi-method measurement of constructs. We will compare the efficacy of BMI+SC versus SC across two groups: a) individuals with low/moderate affective psychopathy (affective score < 5) and, b) individuals with high affective psychopathy (affective score > 5). In Session One, individuals who are within their first three weeks at MCPS will be recruited and briefly screened for substance use. Individuals who report substance use once per week or more and meet the Drug Abuse Screening Test cutoff score of 3 or higher⁵¹ will continue in the study. Session Two (Baseline Assessment A) will involve a brief assessment of general psychopathology and detailed assessment of psychopathy and frequency of use of a range of substances. Baseline assessment B will include assessment of putative mediators (self-regulation and commitment to change), along with an assessment of treatment services use over the past 6 months. After Baseline Assessment B, participants will be randomized (coin toss) to either BMI+SC or SC in pairs that are matched according to affective psychopathy level. That is, two individuals with low/moderate affective psychopathy will be randomized (one each) to either BMI+SC or SC. The same will occur with individuals who are high in affective psychopathy. The next session will occur as close to baseline as possible, followed by sessions at 2, 4, and 6 weeks post-baseline. These meetings will involve assessments of frequency and type of substance use (both groups), and the delivery of our BMI (treatment group only). The outcome variables will be 1) frequency of substance use (proximal; percent days abstinent at 6 months) and 2) violent criminal recidivism (distal; charges at 12 months).

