D.3.1. Sample. A total of 536 participants will be recruited and randomized to either the BMI+SC or SC condition during the first four and a half years of the study. The proposed sample size is feasible based preliminary data (i.e., approximately one eligible participant per recruiting day). We will screen approximately 545 participants per year (in 1:1 format). Based on preliminary data, 22% of these participants ($n=119$) will meet eligibility criteria for the study. We estimate attrition during follow-up at approximately 25% based upon Preliminary Study 2, leaving approximately 91 participants per year (or a total of 416 across 4.5 years) for analysis.

D.3.2. Rationale for standard care control group. Ultimately it is important to determine whether the BMI is efficacious relative to a specific active comparison condition. However, it is first necessary to determine whether the BMI+SC works at all compared to SC, taking into account affective psychopathy scores. Approximately 50% of all MCPS clients are mandated through the court system to complete substance abuse treatment, though the number who do so is lower. For the proposed study, the SC condition will include individuals who receive levels of non-study intervention that vary widely, from none to substantial. This real world condition provides the potential for useful generalization of results to other supervision programs, and is an appropriate comparison for assessing a brief intervention that may best serve as an adjunct to SC. The SC condition will consist of no research-related intervention beyond the baseline assessment session, but we will measure and analyze all non-study treatment participation carefully. Individuals in MCPS do not receive substance use services onsite, though some are referred to community providers for treatment. For anyone involved in non-study treatment, we will measure number of sessions and type of treatment in order to ensure that comparisons between BMI+SC and SC take into account all extra-study treatment.

D.4. Overview of Study Appointments

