D.4.3. Sessions 2 and 3: Baseline Assessments A and B. Participants who qualify will complete two baseline assessment sessions, scheduled within one week of each other, to gather thorough multi-method data while minimizing subject burden. For *Baseline A* we will administer the Timeline Followback Interview (TLFB)⁵⁷ to measure drug and alcohol use frequency in the past 90 days and the 125-item PDSQ⁵¹ to screen for mental disorders. We will then administer a standard psychopathy interview - a semi-structured interview designed to gather information regarding education, relationships, family life, and criminal, medical, and work history. The Psychopathy Checklist-Revised (PCL-R)³¹ will be scored based on this interview and a review of the participant's MCPS file. Following the interview, all participants will receive the names and numbers of drug and alcohol treatment providers, and will be paid \$20 for their time. *Baseline B* will be primarily for the initial assessment of mediators of behavioral change. First, we will administer the Self-Regulation Questionnaire⁵⁸ and the Readiness Ruler.⁵⁹ Participants will then complete a behavioral task – the Balloon Analogue Risk Task (BART)⁶⁰ as a second method of assessing self-regulation. Finally, we will gather extensive information on nonstudy treatment utilization using the Economic Form-90,⁶¹ a valid interview that obtains information about recent health services use. This will include treatment type (e.g., medication vs. psychosocial, individual vs. group, and substance use vs. mental health). This information will be supplemented with information on treatment modality collected from area substance use treatment centers. For example, of the four service providers contacted by the P.I. since the initial submission, all provided data on modality (12-step/abstinence based vs. cognitive behavioral or integrative). Following Baseline B, participants will be randomized in matched pairs – based on affective psychopathy group – to BMI+SC or SC.

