change and self-regulation as mechanisms of change. Commitment to change. 1) We will code change talk that occurs in BMI sessions using the Client Language Easy Rating (CLEAR) coding sheet.⁶⁹ Audiotaped sessions will be transcribed and coded for the proportion of participant change talk: change talk/(change talk+sustain talk+neutral), yielding the percentage of speech utterances that are change talk. 2) The readiness ruler, an efficient and reliable measure of motivation to change⁵⁹, will be used at baseline and following each intervention session for an assessment of readiness to change. Self-Regulation. The Self-Regulation Questionnaire⁵⁸ will be administered during the screening session and after each intervention session to assess increases in self-regulation that have occurred. The BART,⁶⁰ a computerized behavioral task, will provide a second method of assessing self-regulation and will be administered after the last intervention session.

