D.6. Personnel and training. The multidisciplinary research team from Preliminary Study 2 remains intact, including the study coordinator ([name], BA), and the study therapist ([name]., LCSW). During the first year of the award period, the P.I. (a psychologist with extensive experience with M.I.) will hire a third therapist in order to ensure that we adequately study any therapist effects. The P.I. will conduct training on the BMI that involves four, four-hour seminars. Materials will include Miller and Rollnick's text on MI¹⁵ and the intervention manual (Appendix B.) The P.I. will then conduct therapist BMI training sessions at MCPS. The Motivational Interviewing Treatment Integrity (MITI) code⁷⁰ will be used to assess treatment fidelity during these observations. The MITI measures therapist behaviors, yielding both global scores and behavior counts that indicate whether a therapist is delivering an MI-consistent intervention. Once each therapist demonstrates adequate treatment adherence for three straight observed sessions, he or she will begin conducting sessions alone. The P.I. will serve as the primary clinical supervisor for [name] and an additional therapist, and will conduct a minimum of 20% of BMI sessions. The project coordinator has extensive training in all baseline assessments and how to assign subjects to treatment conditions. New personnel will receive intensive PCL-R training from the P.I. Psychopathy interviews will be audio-recorded in order to measure interrater reliability and BMI sessions will be audio-recorded to assess MI-related fidelity and provide data for the linguistic analysis of change talk.

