**Brief Intervention for Justice-Involved Substance Users:
Harnessing Mechanisms of Change**

NCT03308877

04/01/2017

D.7. Data Analysis. A baseline check of randomness will be conducted for each variable collected. Categorical variables will be analyzed using chi-square tests; continuous variables with ANOVAs. To assess Hypothesis 1 continuous outcomes, Analysis of Covariance will be used. The effects of BMI+SC on commitment to change, self-regulation, and substance use will be assessed immediately following intervention. Longer term substance use effects will be examined at 6-month follow-up. For substance use toxicology results, logistic regression will be used. In all instances, alpha = .05; covariates will include gender, race, age, and the outcome baseline score of interest as well as any other variables found to differ at baseline. Additionally, effect sizes will be examined using marginal means.⁷¹ Structural equation modeling (SEM) will be used to test the hypothesis that the effect of BMI+SC on substance use will be mediated by increases in commitment to change and self-regulation (Figure 2).⁷² *Substance use status* at six month follow-up is the key outcome of interest. We hypothesize that effects on six month substance use are mediated, in part, by BMI+SC effects on commitment to change and self-regulation. Substance use status will be measured using two indicators, percent days abstinent and the urine screen result. *Commitment to Change* will be measured using two indicators at each time point, the Readiness Ruler and the CLEAR change talk score at both baseline and immediate post. Two indicators will also be used to assess *Self-Regulation* at baseline and immediate post: Self-Regulation Questionnaire scores and Balloon Analog Risk Task scores. Additionally, demographic variables will be statistically controlled for in the model (gender, age, race, ethnicity). The MPLUS statistical package⁷³ will be used for SEMs. To provide a metric for each latent construct and to identify the model, the first construct loading for each latent variable will be set at 1.0. A two-step approach examining the model will be undertaken.⁷⁴ First, using confirmatory factor analytic techniques, a test of the proposed measurement model will be conducted and any needed modifications to this model, including testing for measurement invariance over time, will be undertaken prior to examining model fit. The second step involves an examination of the structural portion of the model. The model suggests that BMI effects on substance use are not only direct, but also indirect, mediated by effects on commitment to change and self-regulation. Baseline substance use status, commitment to change, and self-regulation will be controlled for, aiding precision in detecting treatment effects. Fit of the model will be assessed using a chi-square statistic, as well as the more approximate fit indices of the root mean square error of approximation (RMSEA),⁷⁵ the comparative fit index (CFI),⁷⁶ and the standardized root mean square residual (SRMR). Using various cutoffs for fit assessment helps to minimize Type I and Type II errors.⁷⁷ Recommendations that adequate fitting models have $CFI > .95$, $RMSEA < .06$, and $SRMR < .08$ will be adopted here. BMI indirect effects on 6 month substance use will be tested using the bias-corrected confidence limits.⁷⁸ Significance will be assessed by whether or not the 95% confidence limits contain zero. The bias corrected approach has been shown to provide the most accurate confidence limits and greatest statistical power when compared with other existing approaches for detecting mediation.⁷⁸ Multi-group structural equation modeling will be used to test moderated mediation. Two groups (high vs. low/moderate on affective psychopathy) will be compared. We will isolate differences across models by first examining if measurement parameters are equal across groups. Model differences across groups will be tested using the chi-square difference test. Next, we will test for structural differences across groups, examining regression parameter estimates for equality, followed by an examination of latent variables' variances and means across the groups. Such moderated-mediation will allow for isolation of BMI effects on latent variable means, controlling for process differences across the groups. Four exploratory analyses will also be conducted. The first will examine longitudinal change in substance abuse using growth curve analyses. Substance use is measured at baseline, 4 times during the intervention period, and at 6-month follow-up (6 time points). Time will be modeled so that the intercept reflects baseline status and subsequent time points will be modeled as weeks from baseline. Both linear and curvilinear (quadratic) change

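### The commitment factor in the mediation SEM needs CLEAR change talk at baseline and post in both arms, but the only CLEAR source described is BMI sessions, held after randomisation and in one arm

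*SAP*

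**What the plan says.** - **Role of CLEAR.** SAP D.7 gives the commitment factor "two indicators at each time point, the Readiness Ruler and the CLEAR change talk score at both baseline and immediate post". The model tests whether the BMI+SC effect on six-month use runs through commitment and self-regulation. It states that "Baseline substance use status, commitment to change, and self-regulation will be controlled for", and the measurement step includes invariance over time.
- **Source of CLEAR.** Protocol D.5.2: "We will code change talk that occurs in BMI sessions using the Client Language Easy Rating (CLEAR) coding sheet". D.6 agrees: "BMI sessions will be audio-recorded to assess MI-related fidelity and provide data for the linguistic analysis of change talk".
- **Who has BMI sessions.** Protocol D.3 lists, for the meetings after randomisation, use assessments in both groups "and the delivery of our BMI (treatment group only"). D.3.2 adds: "The SC condition will consist of no research-related intervention beyond the baseline assessment session".
- **When they occur.** Protocol D.4.3: "Following Baseline B, participants will be randomized in matched pairs". Of the first BMI or assessment meeting, D.3 says: "The next session will occur as close to baseline as possible".
- **Other measures.** Baseline B (D.4.3) has the Self-Regulation Questionnaire, the Readiness Ruler and the BART, with no sample of change talk. The psychopathy interviews are also recorded (D.6), but for interrater reliability.

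**The concern.** An indicator in a two-arm SEM has to be observable in both arms if it is to inform the treatment effect on its factor. A baseline covariate has to be fixed before treatment starts. As described, CLEAR meets neither condition.

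Reading baseline as the first BMI session does not repair this. That session is already treatment, so adjusting for it would adjust for something treatment can change, and SC has no such session.

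Commitment is one of the two mechanisms the trial sets out to test. The same SEM is reused for violent recidivism and for the psychopathy, gender and race comparisons (SAP D.7), so the problem carries into each. The clause in D.7 that allows needed modifications to the measurement model names no replacement. The mediator would then be redefined after the data are in hand.

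**Working it through.** **1. The plan's own SEM figure.** D.7.1 states fit power at n = 416 and 94 df. With noncentrality λ = (N − 1) × df × RMSEA² and alpha .05:
- Null RMSEA .08, true .05: λ = 415 × 94 × .0064 = 249.7 under the null and 415 × 94 × .0025 = 97.5 under the alternative. Power is .9998 (stated: above .95).
- Null RMSEA .05, true .01: λ = 97.5 and 3.9. Power is .9996 (stated: .99).
- At n = 300 the two values are .996 and .986 (stated: above .90).

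The stated power reproduces. It describes global fit only and takes every indicator as observed on all 416.

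**2. CLEAR values that can exist** (416 analysed, 208 per arm, two time points: 416 × 2 = 832 planned).

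| Reading of baseline | BMI+SC | SC | Total |
|---|---|---|---|
| Before randomisation | 0 + 208 | 0 of 416 | 208 of 832 (25%) |
| First BMI session | 208 + 208 | 0 of 416 | 416 of 832 (50%) |

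The 208 is tied to the analysed sample. About 536 / 2 = 268 are randomised to BMI+SC, so the count could be higher. If all randomised in both arms are used, the first-row share is the same: 268 / (536 × 2) = 25%. Missed sessions lower the count, and BMI sessions are not held in jail (Protocol D.4.5).

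**3. Treatment-to-commitment path.** CLEAR is seen at only one value of treatment, so its covariance with treatment cannot be estimated. In a model with the Ruler in both arms and post CLEAR in BMI+SC only, the standard error of this path is √(2/208) = .098 Ruler SD with or without CLEAR. Adjusting for a baseline Ruler correlated .5 (assumed) gives .098 × √(1 − .25) = .085. Either way the information comes from the Ruler.

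**4. Imputing CLEAR in SC.** Imputation from the Ruler returns the Ruler effect times the Ruler-CLEAR correlation. With an assumed Ruler effect of .2 SD and correlations of .2, .4 and .6, that is .04, .08 and .12 SD. Simulation gave these values whether the true CLEAR effect was 0, .3 or .6 SD.

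**5. What CLEAR can still do.** The model in step 3 is identified (11 parameters, information matrix rank 11). Within BMI+SC, CLEAR informs Ruler error and so the commitment-to-use path. The table shows a simulation with 208 per arm, assumed Ruler reliability .6, CLEAR loading .3 to .7 and a true indirect effect of .090.

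| Approach | Mean estimate | SD |
|---|---|---|
| Post CLEAR in BMI+SC only | .091 to .099 | .046 to .073 |
| Ruler entered as observed | .051 to .053 | about .025 |

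A single-indicator Ruler with reliability fixed at .8 when the truth is .6 gives about .090 × .6 / .8 = .068.

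**6. Cost of an uncorrected Ruler.**
- *Commitment.* The indirect effect shrinks by the reliability, so to 60% to 90% of its size for an assumed reliability of .6 to .9. With baseline-post correlation r the factor is (reliability − r²)/(1 − r²). At r = .5 it is (.6 − .25)/.75 = .467 to (.9 − .25)/.75 = .867.
- *Self-regulation.* Assume equal mediator slopes, Ruler reliability .6 and mediator residual correlation ρ. The indirect effect is multiplied by (1 + ρ)(1/.6 − ρ)/(1/.6 − ρ²), which is 1.127 at ρ = .3 and 1.235 at ρ = .5. A true .090 becomes .101 or .111.

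**7. Fit power after a change.** The revised df cannot be derived without Figure 2. At n = 416 the lower of the two powers is .976 at 50 df, .990 at 60, .997 at 74 and .999 at 87.

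**The case against.** **The missing appendices.** Protocol D.4.1 refers to Appendix C for the measures and timeline, SAP D.7 refers to Figure 2, and neither was available. D.5.2 does not say that CLEAR is coded from BMI sessions alone. This stands as a limit on certainty: a reader might infer that SC certainly has no CLEAR data, but the documents support only that no source is described. An appendix that supplied one would have to depart from D.5.2 and D.6.

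**A one-arm indicator is legitimate.** This also stands. A reader might infer that keeping CLEAR in BMI+SC requires CLEAR to behave the same way in SC. It does not, because the SC likelihood then has no CLEAR term. The model needs equal Ruler measurement and an equal commitment-to-use slope across arms. Nor must CLEAR be removed altogether, since it is the only planned second commitment measure that informs Ruler error.

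**Imputation is not planned for this model.** D.7.1 attaches multiple imputation to analyses of mean and rate differences, and D.7 does not say that CLEAR enters the ANCOVA. Step 4 is therefore a warning about a possible rescue, not a fault in a stated analysis.

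**The primary results do not use CLEAR.** That is correct for percent days abstinent and violent charges. It limits the reach of the problem but does not make the mediation model runnable.

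**Conclusion.** The SEM is wrong as written and needs correcting before the mediation analysis. On the supplied text, the two-indicator baseline commitment factor, its invariance test and any between-arm CLEAR comparison cannot be carried out. About 25% of the planned CLEAR values can exist, or 50% on the lenient reading, and none is in SC. These counts assume 416 analysed and equal arms.

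Three stronger readings are not supported:
- *Mediation through commitment cannot be estimated.* It can, if the Ruler is collected in both arms after baseline.
- *SC lacks a post-baseline Ruler.* This is unproven. D.5.2 ties the Ruler to baseline and intervention sessions, and the Week 6 sentence in D.4.4 does not name it. But D.4.4 also gives both arms the same number of assessments, and Appendix C may settle the matter.
- *The sample size must change.* Fit power stays high over the df range examined.

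The opposite error is to treat the self-regulation path as insulated. It can shift if the Ruler enters with uncorrected error and the mediators are correlated. The reliabilities, correlations and effect sizes above are assumptions, because the documents give none.

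**What to change.** 1. Delete baseline CLEAR from the SEM and make no between-arm CLEAR comparison. Use the Readiness Ruler at baseline and post as the between-arm commitment measure.
2. Prespecify one option:
   - **(a)** Drop CLEAR from the two-arm SEM. Model the Ruler as a single-indicator latent variable with a prespecified reliability and a sensitivity range. Analyse CLEAR within BMI+SC only, as a predictor of six-month use, and state how missed sessions are handled.
   - **(b)** Keep post CLEAR as an indicator in BMI+SC only. State the two equality assumptions named above, and that CLEAR informs Ruler error and the commitment-to-use path but not the treatment-to-commitment path.
3. Confirm in Appendix C that SC completes the Ruler after baseline. If not, add it to the existing Week 6 assessment in both arms. This check comes first, because an uncollected value cannot be recovered.
4. Restate the SEM df and fit power for the revised model.

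The cost is SAP rewording and, only if needed, one short self-report at a visit both arms already attend. Commitment loses its second measurement method between arms. The result then depends on an assumed Ruler reliability under (a), or on a noisier estimate under (b).
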